9.3 Recruitment Strategy

Participants will be recruited via printed advertisements, posters and flyers distributed throughout UNSW and the surrounding general communities of Kingsford and Randwick, and those interested in participating will contact the research team via telephone or email provided in the printed adverts.

A digital format of this advertisement will be posted as a link on the UNSW School of Optometry and Vision Science website, circulated via screen advertising in the school and clinic, and emailed to the school staff and students. Email invitations will be sent individually to previous participants who have expressed interest in participating in future studies. Emailed recipients will not be able to see the contact details of others on the distribution list.

On all recruitment posts, the key inclusion criteria of age (at least be 18 years old) and current active allergic conjunctivitis symptoms and signs will be emphasised. It will explicitly acknowledge that if participants are interested in taking part in the research, they will need to initiate contact with the research investigators via email. Those interested in the study will be provided with a copy of the Participant Information Statement and Consent form by email.

9.4 Screening

The first email exchange between participants and the research investigators will entail a copy of the Participant Information Statement and Consent Form, which demonstrates the screening procedure, and key inclusion and exclusion criteria outlined in section 9. Once they pass the screening procedure, a date will be set for the participant visit. The participants will read and sign the informed consent form prior to data collection. Ineligible subjects will be notified and excluded from the study immediately. For participants who withdraw their study consent, no additional data will be collected. However, measurements and confocal microscopy collected before the withdrawal will be retained and analysed.

Screening process:

After participants have contacted the investigators regarding their interest, an email will be sent to the participants as part of a screening procedure. This will include questions regarding the key inclusion and exclusion criteria.

The investigators will conduct two eligibility phases (phase 1: eligibility questionnaires and phase 2: eligibility confirmation by the Skin Prick Test results) on the screening day. Phase one takes place at the School of Optometry and Vision Science, UNSW. The investigator will ask questions about ocular allergy or hay fever symptoms including itchiness and watery eyes, sneezing, or running nose, and interested participants will be asked to answer additional questionnaires to assess their eligibility for the study. They will take part in a preliminary examination which includes visual acuity assessment and ocular health check in order to exclude undiagnosed eye diseases.

In the second phase, a Skin Prick Test which takes approximately 15 minutes to complete will be conducted on the same visit day, under medical supervision at the UNSW Health Service After determining the eligibility of the participants and signing of the consent form. Included participants will be asked to complete a washout period of 1 week duration for which they will be given commercially available ocular lubricant eyedrops (Blink Intensive Tears eyedrops, ARTG ID:158805) and will be asked to install two drops daily in both eyes for 1 week. Eligible participants with active allergic conjunctivitis based on current active allergic conjunctivitis symptoms (including itchiness or watery eyes or burning feeling or feeling like there is dirt or grit

in your eyes) or signs (including redness or swollen eyelids), with or without a prior diagnosis of ocular allergy or hay fever will be randomly assigned (based on a computer-generated list) to 3 groups to receive either topical antihistamine and mast cell stabiliser eyedrops (dual-acting agent), or corticosteroid eyedrops in the treatment group, or lubricant eyedrops as the control group. Intervention categories will be pre-packed in sealed envelopes and randomly labelled (intervention A, intervention B, and intervention C). Each envelope will have a sufficient amount of dosage for the treatment period.

All the clinical tests will be conducted at the School of Optometry and Vision Science, UNSW. The skin prick test will be conducted at the University Health Service, UNSW, located at the Kensington campus with access to medical care in an unlikely event of an emergency.

9.5 Consent

A consent form and participation information sheet will be provided to the participants after they have initiated contact with the research investigators regarding their interest in participation. This information will detail the entire research including the purpose, research participating hours, risks involved, reimbursement, participant confidentiality and contact details of the investigator. There will be no coercion as the potential participants will be obtaining information of the study from posters on the bulletin board or from pamphlets given to them after their consultation in the UNSW clinic. They will also be reminded that their participation is completely voluntary, and they can withdraw at any time.

9.6 Withdrawal of Consent or Participant

- The participants have the right to withdraw from the trial at any time for any reason, without the need to justify their decision. However, the Investigator should record the reason for the patient's withdrawal, if possible. The investigator also has the right to withdraw participants.
- Participants will be withdrawn in the following circumstances:
- A participant's desire to withdraw for any reason.
- Loss to follow-up (every effort must be made to contact the participant; a certified letter must be sent or phone calls)
- An adverse event which, in the opinion of the Investigator and/or Sponsor, necessitates withdrawal.
- A participant's substantial non-compliance (e.g., visits non-compliance) after the start of the trial.
- The investigator's opinion that continuing the participant in the trial is not appropriate. The investigator may withdraw a participant at any time if it is considered to be in the participant's best interest.
- Participants suffering a worsening in disease are to be withdrawn. Worsening will be defined as an increase from the last visit in symptoms and signs score. Such worsening should be evaluated by the investigator and confirmed by slit lamp examination (no improvement or worse symptoms and signs) prior to deciding whether or not to withdraw the patient.

In case the participant has withdrawn consent, no new data can be entered into the record form. Any withdrawal must be fully documented in the report form and registered in as discontinued. If the reason for discontinuation is an adverse event, the specific event will be recorded in the report form. Withdrawn participants will not be replaced.

In case the investigator becomes aware of any serious adverse events (SAEs) or related non-serious adverse events in a withdrawn participant after trial completion these will be reported to HREC.

HREC may temporarily or permanently discontinue the trial at an investigational site at any time for safety, ethical, compliance or other reasons. If this is necessary, HREC will endeavour to provide advance notification to the site. If the site or trial is suspended or discontinued, the Investigator/Investigative Staff will be responsible for promptly informing HREC that this has happened.

10. Treatment of Subjects

Participants will undergo the following procedures:

- **Skin Prick Testing:**

This test is for the confirmation of allergy eligibility as set by the inclusion criteria and will be conducted at phase two of the eligibility examination as described in section 10.4. A standard Skin Prick Test for common Sydney-based region indoor and outdoor aeroallergens will be conducted on each participant using extracts of ten chosen allergens (Stallergenes, Antony, France). Allergens will include four grass pollens (Rye: *Lolium perenne*, Bermuda: *Cynodon dactylon*, Paspalum: *Paspalum notatum* and Johnson: *Sorghum halepense*), two tree pollen (Cypress: *Cupressus arizonica* and Olive: *Olea europaea*), two dust mites (DP: *Dermatophagoides pteronyssinus* and Farinae: *Dermatophagoides farinae*), plant pollen (Plantain: *Plantago lanceolata*), the mold *Alternaria* and cat and dog dander.

A drop of each allergen will be placed on the forearm, and a slight skin prick will be made using a lancet at the same spot to allow the allergen to be absorbed by the skin. Ten minutes later, the skin's allergic reaction will be determined by measuring the size of the hive formed on the skin.

- **History taking:**

A review of demographics, ocular and medical history will be conducted verbally.

- **Questionnaires**

Participants will be asked to complete questionnaires related to eye and nose allergy symptoms and participants' quality of life: Numerical Rating Scale (NRS) [1, 2], Mini Rhinoconjunctivitis Quality of Life Questionnaire (Mini-RQLQ) [3], Ocular Surface Disease Index (OSDI) [4], Aston University Allergy Questionnaire (AUAQ) [5], the dry eye questionnaire for the detection of dry eye (Dry Eye Questionnaire: DEQ-5) [6], and the Eye Allergy Patient Impact Questionnaire (EAPIQ) [7]. Changes in symptoms and signs will be recorded, reported and analysed from both eyes as appropriate.

- **Visual acuity assessment**

Measurement of the standard of vision achieved with the participants' usual spectacle correction in place (if any), will be measured using standard letter charts. Measurements will be taken separately for each eye. Pinhole acuity will be attempted for those without 6/6 vision.

- **The Perkins Tonometer**

The Perkins tonometer is a handheld applanation model used to measure intraocular pressure. The principle of applanation tonometry is based on the force required to flatten a certain area of the spherical surface of the cornea is the same as the pressure inside the eye. The Perkins tonometer is a very popular handheld applanation tonometer used in humans.

- **The Oculus Keratograph 5M (K5)**

This is an advanced corneal topographer with a built-in real keratometer and a colour camera optimized for external imaging. In our study the tear film break-up time will be measured automatically and non-invasively.

- **Slit lamp biomicroscopy**

The ocular surface and anterior segment will be examined using a slit lamp biomicroscope and ocular surface signs, including conjunctival and limbal redness (graded using the Cornea and Contact Lens Research Unit (CCLRU) grading scale), conjunctival chemosis, papillae and follicles (graded using the Japanese grading scale for allergic conjunctivitis [8]).

- **Ocular staining**

A wetted fluorescein strip (harmless yellow dye) and a wetted lissamine green strip (harmless green dye) will be then gently touched to the fornix of the lower lid. Participants will be asked to blink continuously to enable the smooth spreading of the stain over the eye, allowing for the evaluation of any surface defects. Ocular surface (corneal and conjunctival) staining will be assessed using the Oxford grading scale [9]. These dyes are routinely used in optometry practices worldwide and are safe to use.

- **Confocal microscopy**

A confocal microscope will be used to visualise the corneal sub-basal corneal nerves and dendritic cell in vivo. A probe that emits harmless laser light will come in contact with the transparent front part of the eye for approximately 5 minutes, and microscopic images of the cornea will be captured. Images will be captured from the right eye only. To avoid any discomfort to the patient or causing abrasions on the transparent surface of the eye a topical anaesthetic will be installed in the tested eye and a soft lubricating gel will be applied over the microscope probe.

All the above-mentioned clinical procedures (except the Skin Prick Test) will be repeated for the eligible participants at the follow-up visits.

Reference list

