All study groups will undergo the same measurements and test procedures (Table 1). Participants using eye and/or general medication known to affect eye health or eye comfort before or during the study will be excluded. The personnel to whom the above listed responsibilities are delegated should be trained clinicians.

	Visits							
	Visit 1 (2 hours)	Treatment visits (14 days)					Post-treatment visits (14 days)	
Conducted procedure (Approximate time)		Visit 2 (1 hour)	Visit 3 (1 hour)	Visit 4 (1 hour)	Visit 5 (1 hour)	Visit 6 (1 hour)	Visit 7 (1 hour)	
Medical history	X							
Questionnaires and record forms	X	X	X	X	X	X	X	
Skin prick test	X							
Visual acuity		X	X	X	X	X	X	
Perkins Tonometer		X	X	X	X	X	X	
The Oculus Keratograph 5M (K5)		X	X	X	X	X	X	
Slit lamp examination		X	X	X	X	X	X	
Ocular staining		X	X	X	X	X	X	
Confocal microscopy		X	X	X	X	X	X	

Table 1: Table of Procedures

15. Safety and Monitoring

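### Withdrawal for worsening needs only some rise in a secondary-endpoint score and has no stated follow-up, so later visits would be lost depending on outcome, probably unequally by arm

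*Protocol*

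**What the plan says.** **Trigger.** Section 9.6 states that "Participants suffering a worsening in disease are to be withdrawn", and then: "Worsening will be defined as an increase from the last visit in symptoms and signs score". The comparison is with the previous visit, not baseline. No minimum rise is given. No score is named, although Section 10 collects six questionnaires and several graded signs.

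**Confirmation and decision.** The investigator first assesses the worsening; the text then asks for it to be, in its words, "confirmed by slit lamp examination (no improvement or worse symptoms and signs) prior to deciding whether or not to withdraw the patient".

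**Consequence.** Withdrawal is registered as discontinuation, and "Withdrawn participants will not be replaced". For withdrawal of consent, Section 9.6 says "In case the participant has withdrawn consent, no new data can be entered into the record form", and Section 9.4 says that "measurements and confocal microscopy collected before the withdrawal will be retained and analysed". Neither section says whether someone withdrawn for worsening, who still consents, attends the remaining visits.

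**Medication.** Section 14 adds: "Participants using eye and/or general medication known to affect eye health or eye comfort before or during the study will be excluded". It does not say whether exclusion is from drops, visits or analysis.

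**Endpoints and analysis.** Section 4 makes dendritic cell density the primary endpoint, lists changes in symptoms and signs among the secondary endpoints, and gives the time course as an aim. Section 14 schedules visits at 24 hours and days 7, 14, 21 and 28. Section 18 compares symptoms and signs by t-test or Mann-Whitney test, and density by a linear mixed model.

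**The concern.** The variable that triggers withdrawal is of the same kind as the secondary outcomes. With no margin above ordinary visit-to-visit variation, the rule can fire on noise. It fires more often in participants who are not improving than in those who are. If treatment works, loss will differ by arm.

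A rise in scores after the drops stop is part of the time course that days 21 and 28 are there to record. Such a rise also meets the definition of worsening, so a rise at day 21 can cost the day-28 visit.

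The medication clause also acts after randomisation and may depend on how the participant is doing. A two-group test on observed cases does not correct for loss of this kind, and no later analysis plan can recover visits that never took place.

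**Working it through.** **1. The plan's own allowance (Section 8).** 25 per arm × 1.2 = 30, and 3 × 30 = 90. The stated loss from all causes is 20%. (Completing 75 of 90 allows 15 losses, or 16.7%; 20% of 90 is 18, leaving 72. This is noted only as the yardstick.)

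**2. Exact case.** Assume one continuous score, no true change, and exchangeable errors across baseline and k follow-up visits. A participant is never flagged only if all k + 1 values fall in strictly descending order, which has probability 1/(k + 1)!.

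- By day 14 (k = 3): 1 − 1/24 = 95.8%.
- By day 28 (k = 5): 1 − 1/720 = 99.9%.

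**3. Coarser scores, three readings, partial action on flags.** The documents give neither the score nor its variability, so these are assumptions: integer scores, independent visit noise of SD 1, and symptom and sign scores independent of each other. "Flat" means no true change. "Improving" means the mean falls 1 SD at each on-treatment visit (3 SD in all by day 14) and then stays level. Each flag is acted on with a fixed probability. Entries are the share withdrawn at or before the visit.

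| Reading of the rule | Flags acted on | Day 14, flat | Day 14, improving | Day 28, flat |
|---|---|---|---|---|
| Single score rises | all | 85% | 42% | 97% |
| Symptom rise, sign not improved | all | 60% | 16% | 80% |
| Both scores rise | all | 37% | 7% | 55% |
| Single score rises | one in four | 26% | 11% | 39% |
| Symptom rise, sign not improved | one in four | 17% | 4% | 27% |
| Both scores rise | one in four | 10% | 2% | 16% |

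If one flag in ten is acted on, the flat figures for a single score are 11% by day 14 and 17% by day 28. With both scores required, the day-28 figure is about 7%.

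**4. A smaller treatment effect.** Take continuous scores with a total improvement of 1 SD by day 14 and intraclass correlation 0.7. Flagged by day 14, flat versus improving: 96% versus 79% on a single score, and 64% versus 32% if both must rise. Over intraclass correlations of 0.5 to 0.9 the gap is about 12 to 35 points (single) and 25 to 46 points (both).

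**5. Effect on a score comparison** (same model, intraclass correlation 0.7, single score). If every flag is acted on, the observed day-14 mean change is −0.47 SD where the truth is 0, and −1.30 where the truth is −1.00. The arm difference is then 1.30 − 0.47 = 0.83 SD instead of 1.00. If one flag in four is acted on, the means are −0.04 and −1.04, and the difference is 1.00, almost unbiased.

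**6. What is lost.** A participant flagged at a visit has already been measured there; the later visits are missing. In the model of step 5 with one flag in four acted on, 57% of flat and 66% of improving participants still have a day-28 value, so 43% and 34% do not.

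**The case against.** The strongest reply is that Section 9.6 is sequential and leaves room for judgement: a score rise, then evaluation, then slit-lamp confirmation, then a decision whether or not to withdraw. That stands. A reader might infer that any rise removes the participant automatically, or that lack of improvement alone is a trigger; the text supports neither. Lack of improvement appears only within the confirmation step. It still makes that step weak, because an unchanged eye can confirm a rise.

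A reader might also infer that collected outcomes are deleted. They are not: Section 9.4 keeps data from before withdrawal, although that sentence is written for withdrawal of consent. The problem is data not collected afterwards.

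Nor is it shown that the 20% allowance fails. Among participants with no true change, withdrawal by day 28 runs from about 7% to 97%, depending on which scores must rise and how often flags are acted on.

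Bias in the primary endpoint is uncertain. Section 5 reports no association between changes in density and changes in symptoms or signs. A mixed model using all observed visits is valid if missingness depends only on observed data that the model includes. However, the scores that drive withdrawal are not in the model as described.

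Two further inferences go beyond the text. One is that the medication clause contradicts the washout: Section 9.4 gives the washout lubricant to all included participants and does not tie it to prior use of excluded medication. The other is that withdrawals will concentrate in the active arms after day 14, which no section states.

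**Conclusion.** The point holds in this form. Following the protocol as written, visits after a withdrawal for worsening would go uncollected, and the trigger is a rise of unspecified size in variables that are secondary endpoints. The medication clause can add further loss after randomisation, with its meaning for visits and analysis left open.

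Unequal loss by arm is an expected consequence if treatment improves scores, not something the protocol states. In every scenario run, non-improving participants were withdrawn by day 14 more often than improving ones. The size of the gap rests on assumed noise, the reading of the score, and how often investigators act: with one flag in four acted on it is 26% versus 11%, 17% versus 4%, or 10% versus 2%. Bias in the symptom and sign comparison is material if most flags are acted on and small if few are. Truncated follow-up and lost precision remain either way. For density, the threat is mainly lost precision and an incomplete time course; bias is possible but not demonstrated.

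**What to change.** 1. In Section 9.6, state that stopping study drops is separate from leaving the study. Anyone who has not withdrawn consent continues the scheduled imaging, scores and signs and is analysed as randomised.
2. Reconcile Sections 9.4, 9.6 and 14 on what being withdrawn or excluded means for visits and for analysis. Medication use after randomisation should be recorded and should not remove the participant from follow-up or analysis.
3. Have the investigators reconcile the definition of worsening with its confirmation wording, and name the score. No clinical threshold or medication rule is proposed here.

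The cost is a short amendment. The visits are already scheduled. The downside is that some will come from participants no longer on drops, so the comparison will reflect allocation to treatment rather than continuous use.

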- Formulation: Prednisolone sodium phosphate 0.5% w/v as well as disodium edetate, monobasic sodium phosphate, sodium chloride, sodium hydroxide and purified water.
- Packaging /units per package: Each unit contains approximately 0.5mL solution in a container that has a twist and pull cap. Each unit should be discarded after a single use. The solution has a neutral pH.
- Storage (incl. specific storage guidance): prednisolone phosphate is stored between 2 - 8°C.
- Market authorisation in Australia: Yes.

The control intervention is an unpreserved lubricant eyedrop (Systane Hydration Unit Dose 0.7 ml).

Systane Hydration Unit Dose 0.7 ml (ARTG ID 308516)

- Active substance: Polyethylene Glycol 400 0.4%, Propylene Glycol 0.3%.
- Manufactured by: Alcon Laboratories Australia Pty Ltd.
- Application form: Topical eyedrop.
- Formulation: Sodium hyaluronate, polyethylene glycol 400, propylene glycol, hydroxypropyl guar, sorbitol, aminomethyl propanol, boric acid, sodium borate, potassium chloride and sodium chloride.
- Packaging /units per package: Each unit contains 0.7 ml.
- Storage (incl. specific storage guidance): Systane Hydration is stored 5 - 25°C.
- Market authorisation in Australia: Yes.

The washout eyedrops is an unpreserved lubricant eyedrops (Blink Intensive Tears Protective Eye Drops - Unit Dose - Lubricant, eye)

Blink Intensive Tears Protective Eye Drops - Unit Dose - Lubricant, eye (ARTG ID 158805)

- Active substance: Polyethylene Glycol 400 0.25%
- Manufactured by: Johnson & Johnson Surgical Vision Inc.
- Application form: Topical eyedrop.

- Formulation: 0.25% polyethylene glycol 400 (PEG 400), purified water, boric acid, sodium hyaluronate, potassium chloride, sodium chloride, sodium borate, calcium chloride, magnesium chloride.
- Packaging /units per package: Each unit contains 0.4 ml.
- Storage (incl. specific storage guidance): Systane Hydration is stored less than 25°C.
- Market authorisation in Australia: Yes.

Ocular lubricant eyedrops (Blink Intensive Tears eyedrops) will be provided to all participants during the washout period and will be asked to install two drops daily in both eyes for 1 week. All medications used in this trial are unpreserved to minimise the possibility of these preservatives impacting the trial results. Only trained optometrists are to be delegated these responsibilities. All medications given in this trial will be prescribed by registered optometrists.

12. Storage, dispensing and product accountability.

All medications and control eyedrops used in this trial will be stored securely at the School of Optometry and Vision Sciences (Rupert Myers building), with access limited to study investigators. All medications and control eyedrops will only be dispensed to participants who meet the eligibility criteria and are randomised to a treatment group in the trial. The Investigator (or his/her blinded designated personnel) will maintain a participants Medicine Dispensing Log detailing the medication numbers and dates of medication dispensed for each participant during the course of the trial. Only trained optometrists are to be delegated these responsibilities.

Participants will be instructed to discard used medications and control eyedrops in the appropriate way as per manufacturer guidelines. Unused medications and control eyedrops will be destroyed at the trial site in accordance with local requirements and when site operating procedures permits after the drug accountability has been finalised and signed-off by the Investigator.

13. Randomisation and Allocation

This study is a single centre, double-blinded, randomised, placebo-controlled clinical trial. Eligible participants will be randomly allocated to one of the three study groups in a 1:1:1 ratio based on a pre-determined computer-generated list to ensure every participant has an equal chance of being allocated to any treatment arm. All interventions that will be used in this trial will come in transparent ampules. Originally labelled intervention ampules will be masked by covering the drug information with opaque labels. Intervention ampules will be removed from the original packaging and pre-packed in sealed envelopes, and randomly labelled (intervention A, intervention B, and intervention C). Each envelope will have instructions of use and a sufficient amount of dosage for the treatment period. Each group will be randomly assigned to receive either topical antihistamine and mast cell stabiliser eyedrops (dual-acting agent) or corticosteroid eyedrops in the treatment group and lubricant eyedrops as the control group. The pre-packing of the eyedrops will be allocated to external personnel (not a member of the investigators' group). The external personnel will be responsible for maintaining the randomisation list. The randomisation process will be held at the School of Optometry and Vision Science. No specific experience or qualification is required by the personnel delegated these responsibilities.

An emergency decoding possibility, computer-based or other, will be available to the Investigator and to designated investigators. Breaking of the blind for individual patients in emergency situations is an Investigator responsibility. As far as the emergency permits, the need to break the blind will be communicated to HREC. The unblinding in emergency situations is only permitted in case of a suspected, unexpected serious adverse reaction (SUSAR) or other important adverse event, when the knowledge of the trial medications in question is required for

therapeutic decisions for the management of the participant. The Investigator who unblinds a treatment must record the reason and date for unblinding before the treatment code can be broken. The Investigator must record the event of unblinding in the participant's record, including the reason for unblinding, but not the treatment allocation if this can be avoided. In case of accidental unblinding, the same documentation as for emergency unblinding must be obtained.

If HREC needs to unblind a treatment, the reason and the date of opening should be recorded with signature, following standard operational procedures for unplanned unblinding of clinical trial participants. It should be recorded in the subject's source documents that the code is broken, why, when and by whom.

If it is necessary to unblind an individual participant's treatment for the purposes of expedited reporting to the authorities and/or ethics committee, only those individuals whose responsibility it is to report this information will know the identity of the medication. Every attempt will be made to ensure that all other trial and site staff will remain blinded throughout the course of the trial.

Information on whether the blind has been broken for any patients must be collected before the database is declared clean and analysed. No specific experience or qualification is required by the personnel delegated these responsibilities.

14. Treatments, Dosing, Dosage Schedules, and Route of Administration

After taking history, participants will be asked to complete questionnaires (eligibility phase 1), related to eye and nose allergy symptoms: Numerical Rating Scale (NRS), Mini Rhinoconjunctivitis Quality of Life Questionnaire (Mini-RQLQ), Ocular Surface Disease Index (OSDI), Aston University Allergy Questionnaire (AUAQ), the dry eye questionnaire for the detection of dry eye (Dry Eye Questionnaire: DEQ-5) and the Eye Allergy Patient Impact Questionnaire (EAPIQ). Changes in symptoms during the treatment will be recorded using a Numerical Rating Scale (NRS). Changes in symptoms and signs will be recorded, reported and analysed from both eyes as appropriate. Each questionnaire includes detailed instructions on how to complete them. To confirm participants' allergy status, a Skin Prick Test will be conducted (eligibility phase 2) where a drop of allergen will be placed on the forearm, and a slight skin prick will be made using a lancet at the same spot to allow the allergen to be absorbed by the skin. Ten minutes later, the skin's allergic reaction will be determined by measuring the size of the hive formed on the skin. Visual acuity, Tearscope and ocular surface health integrity with white light slit lamp biomicroscopy will follow. Ocular staining will be performed before and after each time taking confocal microscopy images.

Ocular surface dendritic cell images will be taken using the *in vivo* confocal microscopy (IVCM) at the baseline visits and at each follow-up visit. A topical anaesthetic eyedrops will be applied to the examined eye of the participants (right eye) and a soft lubricating gel will be applied over the microscope probe to avoid any discomfort. Participants will be directed to look at a single white fixation light with the contralateral eye to help maintain head posture and eye position. A gentle touch by the IVCM probe will be apply on the corneal surface (the transparent front part of the eye) to capture multiple images from different locations on the cornea.

After the baseline visit, participants will be randomly given either treatment or control eyedrops and instructed to put one drop in each eye, twice daily for two weeks. Participants will be asked to visit the clinic at different interval periods including 24 hours, 7 days and 14 days during the treatment period, and post-treatment at days 21 and 28, to repeat all the examinations except the Skin Prick Test (Table 1).

All study groups will undergo the same measurements and test procedures (Table 1). Participants using eye and/or general medication known to affect eye health or eye comfort before or during the study will be excluded. The personnel to whom the above listed responsibilities are delegated should be trained clinicians.

	Visits							
	Visit 1 (2 hours)	Treatment visits (14 days)					Post-treatment visits (14 days)	
Conducted procedure (Approximate time)		Visit 2 (1 hour)	Visit 3 (1 hour)	Visit 4 (1 hour)	Visit 5 (1 hour)	Visit 6 (1 hour)	Visit 7 (1 hour)	
Medical history	X							
Questionnaires and record forms	X	X	X	X	X	X	X	
Skin prick test	X							
Visual acuity		X	X	X	X	X	X	
Perkins Tonometer		X	X	X	X	X	X	
The Oculus Keratograph 5M (K5)		X	X	X	X	X	X	
Slit lamp examination		X	X	X	X	X	X	
Ocular staining		X	X	X	X	X	X	
Confocal microscopy		X	X	X	X	X	X	

Table 1: Table of Procedures

15. Safety and Monitoring

